## **8.2 Adverse Events**

Individuals receiving the ear acupuncture will be asked about acupuncture-related adverse events at each acupuncture treatment. Any acupuncture-related injuries will be reported to study investigators. Any reported events will be evaluated for the likelihood that they occurred as a result of acupuncture (very likely to be related, likely to be related, possibly related, or unlikely to be related). Patients will also be provided a phone number to contact study staff at DFCI to report potential acupuncture-related adverse events.

Figure 3: Ear acupuncture points

[figure not shown]

Table 2: Ear Acupuncture Points and Locations

Name	Location
Shen men	Superior and central to the tip of the triangular fossa, between the junction of the superior crus and inferior crus of antihelix. It is not at the tip of the triangular fossa, but slightly inward and slightly upward from where the triangular fossa descends from the superior crus toward deeper regions of the triangular fossa.
Point Zero	Notch on the helix root at LM0 (ear center), just as the vertically ascending helix rises from the more horizontal concha ridge.
Kidney	Superior concha, below LM16 (antihelix notch) and superior to the Stomach point. It is often difficult to view this point because it is hidden by the overhanging ledge of the inferior crus.
Liver	Peripheral concha ridge and concha wall, peripheral to the Stomach point.
Stomach	Medial concha ridge, just peripheral to LM0 (ear center) and the central concha ridge.
Esophagus	Inferior concha, peripheral to the Mouth point.

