**Sensory nerve innovations of external ear**

### **3. OBJECTIVES**

1. To evaluate the safety and feasibility of recruiting and retaining breast cancer patients (n = 26), during 3 cycles of adjuvant or neoadjuvant chemotherapy, as measured by rate of recruitment, ear acupuncture compliance, measure collection, and incidences of acupuncture-related side effects during the trial.
2. To collect preliminary efficacy data on ear acupuncture for the reduction of symptom burden (SB) including chemotherapy-induced CINV and anxiety in breast cancer patients, as measured by the *Edmonton Symptom Assessment System (ESAS)*, *State-Trait Anxiety Inventory (STAI)*, the *MASCC Antiemesis Tool (MAT)*, the usage of antinausea medications as well as the ER visits and the hospital admission rate during the trial.

---

 The Multinational Association of Supportive Care in Cancer (MASCC)

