## 5. STUDY DESIGN AND PROTOCOL OVERVIEW

This single arm feasibility study will enroll 26 patients receiving chemotherapy for stage I-III breast cancer. Patients will be enrolled into a single ear acupuncture arm for 3 consecutive chemotherapy cycles. During the first cycle of chemotherapy infusion, participants will receive an educational reading booklet (*Chemotherapy and You* by National Center Institute). During cycles 2 and 3 of chemotherapy infusions, participants will receive a standardized ear acupuncture protocol. Each ear acupuncture session lasts for 30 minutes (Figure 1). The study patients will have an option to continue ear acupuncture treatments with their subsequent chemotherapy infusions but no additional data will be collected. Measurements will be collected at 4 time points in each chemotherapy cycle: Pre-infusion on the Day 1 of chemotherapy, post-intervention on the Day 1 of infusions, on the day after the chemotherapy infusion (Day 2), and on Day 5. Patient-reported outcomes including ***Edmonton Symptom Assessment System (ESAS)***, ***State-Trait Anxiety Inventory (STAI)***, ***The MASCC Antiemesis Tool (MAT)***, anti-nausea medication usage and emergency events diary will be collected. Safety data will be measured using NCI-CTCAE v.4.023 (Figure 2). Measures will be compared between chemotherapy cycles.

Figure 2: Study Schema

 The Multinational Association of Supportive Care in Cancer (MASCC)

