### **8.1 Ear Acupuncture Protocol**

At the infusion during the 1st cycle, the study patients will receive an educational booklet developed by National Cancer Institute. This booklet includes facts about chemotherapy and its side effects. It highlights ways that a patient can care for herself before, during, and after treatment. No acupuncture will be performed during the first infusion cycle. The patient will be encouraged to read the booklet during the infusion. During the second and third infusion cycles, the study patients will receive a 30-minute session of a standardized ear acupuncture treatment.

At each visit, the study patient will be sitting in an infusion chair either reading the booklet (cycle 1) or receiving ear acupuncture treatment (cycles 2 and 3). For each ear acupuncture session, the patient will have ear acupuncture therapy administered to each ear. After the skin of the ear is cleaned with alcohol, six acupuncture needles (SEIRIN®, No. 1., 30 mm x 0.16 mm) will be inserted into acupuncture points bilaterally. The depth of needle insertions is around 2-3 millimeters. Then, acupuncture needles will be gently manipulated to increase stimulation. The patient will be asked to orally report the needling intensity level on a scale from 0-10 (0 being feeling nothing at all and 10 being the strongest one can imagine). Then, the needles will remain in the sites for 30 minutes while receiving IV infusion. After 30 minutes, another round of gentle manual manipulation will be performed prior to the removal of the needles. Figure 3 and Table 2 presents the names and locations of ear acupuncture points.

If a study patient misses an acupuncture treatment, the patient will be asked to make up the missed treatment session during the next chemotherapy infusion, so that a total of 2 consecutive sessions of acupuncture will be provided. The total number of acupuncture sessions received will be recorded for each participant. Any side effects related to the acupuncture will be collected by treating acupuncturists.

An outline of the acupuncture protocol and a summary of acupuncture points to be used are presented below in Figure 3 and Table 2, respectively.

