### 9.2 Expedited Adverse Event Reporting

9.2.1 Investigators **must** report to the Overall PI any serious adverse event (SAE) that occurs after the initial dose of study treatment, during treatment, or within 30 days of the last dose of treatment on the local institutional SAE form.

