## 14.5 Appendix V. Acupuncture Treatment Form

Name of patient: \_\_\_\_\_ Hospital ID# : \_\_\_\_\_ Date of Visit : \_\_\_\_\_

1. Time: Needle Insertions: \_\_\_\_ AM/PM \_\_\_\_ minutes. Needles Out: \_\_\_\_ AM/PM \_\_\_\_ minutes
2. Please make X below to indicate the ear acupuncture points used at today's session, and the points that *De Qi* sensation was obtained.

Points	L	R	Points	L	R	De Qi?	Note				
Shenmen			Kidney			Y	N				
Liver			Point Zero								
Stomach			Esophagus								

3. Please ask the study patient when you have just completed the adjustment of during the treatment session today and make a "X" below:

"Please tell me, on a scale from 0 to 10, the intensity of the needling sensation you are experiencing right now; 0 is that you do not feel anything at all and 10 is the strongest sensation you could imagine."

Intensity Score	0	1	2	3	4	5	6	7	8	9	10
X											

4. At the end of the session, please make "X" below on the patient's immediate responses for today's treatment:

Question Items	Yes	No	Unknown
a Did the patient appear to be relaxed?			
b Was the patient dozed off during the treatment?			
c Was the pulse/heart rate of the patient slower than the beginning of the session?			
d Has the patient's skin temperature of hands noticeably changed (either warmed up or cooled down)?			
e Other observations?			

5. Did the patient report any adverse event per CTCAE v4.0 at this visit?

NO YES, If "YES" is answered, please describe the details here:

Adverse Event	Start Date	Stop Date	Grade (1-5) Mild, Moderate, Severe, Life Threatening, Fatal	Attribution	Comments
Skin bruise				unrelated, unlikely, possible, probable, definite	
Hematoma					
Skin infection					
Presyncope					
Syncope					
Nausea					

6. Was today's session completely followed the study protocol requirement?

Question Item	YES	NO	If "no", please explain here
Was today's session completely followed the study protocol requirement?			

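### No scheduled acupuncture-specific question about non-serious adverse events follows a patient's last session (26 of 52 planned sessions), so delayed local events may be under-ascertained

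*Combined protocol and SAP*

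**What the plan says.** Section 3 makes safety part of Objective 1, measured in part by the "incidences of acupuncture-related side effects during the trial".

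The acupuncture-specific collection is described in three places, all tied to the treatment visit:

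- Section 8.2: "Individuals receiving the ear acupuncture will be asked about acupuncture-related adverse events at each acupuncture treatment".
- Section 8.1: "Any side effects related to the acupuncture will be collected by treating acupuncturists".
- Appendix V, item 5: "Did the patient report any adverse event per CTCAE v4.0 at this visit". The listed terms are skin bruise, hematoma, skin infection, presyncope, syncope and nausea.

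There are two study sessions, in cycles 2 and 3. A missed session is made up at the next infusion, "so that a total of 2 consecutive sessions of acupuncture will be provided". Section 5 lets patients continue acupuncture afterwards, but without further data collection.

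Outside the treatment visit, the plan offers these routes:

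- Section 8.2: "Patients will also be provided a phone number to contact study staff at DFCI to report potential acupuncture-related adverse events".
- Section 9.2.1: serious events are reportable after the first treatment, during treatment, or "within 30 days of the last dose of treatment on the local institutional SAE form".
- Section 9.4: all adverse events go on the toxicity case report forms. No schedule for asking is given.
- Section 5 and Table 1: an emergency events diary and an Event Log column.
- Section 7 and Appendix X: Day 2 and Day 5 home forms, which may be done by phone on patient preference. The phone list is ESAS, STAI, MAT and the medication log.

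**The concern.** Some events on the Appendix V checklist, such as a bruise or a skin infection, can become apparent after the patient has left the infusion chair. The plan's only question aimed at acupuncture effects is put at a session, so it can pick up a delayed event only if another session follows. For the last session none does.

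Incidence of acupuncture-related side effects is a named measure in Objective 1, and the study is meant to inform a later randomized trial. If delayed non-serious events after the last session are recorded only when a patient volunteers them, the reported incidence will tend to be too low. A reader of the results could not tell an absence of events from an absence of asking.

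**Working it through.** The plan states no figure for adverse event ascertainment, so there is none to reproduce. The check is a count, followed by a comparison of the remaining routes.

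**Inputs.** Patients: 26 (Section 5: "This single arm feasibility study will enroll 26 patients receiving chemotherapy for stage I-III breast cancer"). Study acupuncture sessions per patient: 2 (Section 8.1).

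**Count under full compliance.**
- Planned sessions: 26 × 2 = 52.
- Sessions with a same-session question: 52 of 52.
- Sessions followed by a later study acupuncture visit: 26 of 52 = 50%.
- Sessions not followed by one: 26 of 52 = 50%. Every patient contributes one.

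**If *k* patients receive only one session**, the share with no later acupuncture visit is 26/(52 − *k*):
- *k* = 2: 26/50 = 52%.
- *k* = 6: 26/46 = 57%.
- *k* = 8: 26/44 = 59%.

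Provided every patient has at least one session, half is the minimum share.

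**What that could mean in events.** The documents give no delayed-event rate, so I assume a rate *q* per session. Expected delayed events are 52*q*, of which 26*q* follow a session that has a later acupuncture visit.

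| Assumed *q* | Expected delayed events, 52*q* | Followed by a later acupuncture visit, 26*q* |
|---|---|---|
| 2% | 1.04 | 0.52 |
| 5% | 2.6 | 1.3 |
| 10% | 5.2 | 2.6 |

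The difference between the two columns is the number left to the other routes. It is not the number lost, because some will be reported by those routes.

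**The other routes after the last session.**

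| Route | Scheduled? | Specific to acupuncture? | Reaches a non-serious local event? |
|---|---|---|---|
| Phone number (8.2) | No, patient must call | Yes | Yes, if the patient calls |
| Toxicity form duty (9.4) | No asking schedule | No | Yes, if someone learns of it |
| 30-day duty (9.2.1) | No contact scheduled | No | No, serious events only |
| Emergency diary or Event Log (Section 5, Table 1) | Timing not readable | Not known | Not known; Objective 2 names ER visits and admissions |
| ESAS, Day 2 and Day 5 | Yes | No | Possibly, through pain, nausea or the open other-problem item, without attribution |
| MAT, Day 2 and Day 5 | Yes | No | Nausea and vomiting only, without attribution |

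No row is shown to be scheduled, acupuncture-specific and open to non-serious local events all at once.

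**The first session** is covered only by recall. The next acupuncture question comes 14 or 21 days later (Section 4.1), on a form worded around that day's visit.

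**The case against.** The best defence is that the patient is not left unasked after the last session. ESAS is completed on Day 2 and Day 5 of cycle 3 and includes pain, nausea and an open item for another problem. MAT asks about nausea and vomiting. Section 7 has the home forms returned to the study coordinator at the next visit, so a contact is planned. Section 9.4 requires all adverse events on the toxicity forms, and serious events carry a 30-day duty. The Event Log column in Table 1 cannot be read reliably in the text available, and its form is not shown, so it may already contain the missing question. Finally, no feasibility criterion in Section 10.2 depends on an adverse event rate.

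Much of this stands. A reader might infer that delayed events after the last session are never actively sought. The documents do not support that, because the ESAS and MAT items are scheduled prompts. They are not a substitute, however: none mentions the ear or acupuncture, and none carries attribution, which is what Objective 1 needs.

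A reader might also infer that the safety denominator is overstated: with no delayed events found, a one-sided 95% upper bound of 1 − 0.05^(1/52) = 5.6% on all sessions against 1 − 0.05^(1/26) = 10.9% on the sessions with a later visit. The documents do not support this either. The plan states no per-session bound, and Section 10.4 speaks of reporting safety for all patients. With 26 patients as the denominator, zero events already gives 10.9%. The 52-session figure would also treat two sessions in one patient as independent.

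**Conclusion.** The point holds in a limited form. No scheduled acupuncture-specific question about non-serious adverse events follows a patient's last session. That is 26 of 52 planned sessions (50%) under full compliance, and a larger share if some patients have only one session. Same-session ascertainment is planned for all 52 and is not in question.

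The incidence in Objective 1 may be under-ascertained for delayed local events. The size cannot be stated, since the delayed-event rate and the yield of the phone line and general symptom items are unknown.

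The conclusion assumes that the Event Log or emergency diary does not already ask about acupuncture effects. If it does, saying so in Section 8.2 would settle the matter. No feasibility decision changes. This is a cheap improvement to a stated measure, worth making before enrolment.

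**What to change.** 1. Add one item on ear-site and acupuncture-related events to the Day 2 and Day 5 home forms for cycles 2 and 3, and to the phone-survey list in Appendix X.
2. Have the study coordinator review the item when the forms are returned, and ask again then, so that events after Day 5 are also covered. Section 7 has forms returned at the next visit, while the reminder scripts ask for them to be mailed; state which applies.
3. Tie the item to the session as well as the cycle number. A session made up after cycle 3 would otherwise fall outside the Table 1 schedule.
4. Enter positive answers on the toxicity form with grade and attribution. First reconcile the attribution scales: Section 8.2 has four levels, while Section 9.1 and Appendix V have five.
5. State in Section 8.2 what the Event Log collects.

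The cost is one extra item per form for patients and a little staff time to grade and attribute positive answers. Phone completion is by patient preference, so most of the gain rests on the paper forms. No new visit is needed. With complete returns, sessions with a later acupuncture-specific question would rise from 26 of 52 to 52 of 52. Without step 2, events arising after Day 5 of the last session would still go unasked.

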## **7. SPECIMEN/DATA COLLECTION PROCEDURES**

The pre-infusion assessments will be collected before patients are given educational materials (cycle 1) or receive acupuncture (cycles 2 and 3) on Day 1 of cycles 1-3. The post-intervention assessments will be repeated after the completion of reading educational material or acupuncture on Day 1, Day 2 and Day 5 of cycles 1-3.

Study measures will be collected according to the following schedule (Table 1):

Table 1. Schedule of Study Measures

	Tracking Log	Consent Form	Educational Booklet	ESAS	STAI	MAT	Medication Log	Event Log	AES	Acupuncture Tx Form
Recruitment	X	X					X			
Cycle 1				X	X	X				
Pre-Intervention	Day 1			X						X
Post-Intervention	Day 1			X		X				
	Day 2			X		X				
	Day 5			X		X			X	
Cycle 2				X		X				
Pre-Intervention	Day 1			X		X				X
Post-Intervention	Day 1			X		X				
	Day 2			X		X				
	Day 5			X		X			X	
Cycle 3				X		X				
Pre-Intervention	Day 1			X		X				X
Post-Intervention	Day 1			X		X				
	Day 2			X		X				
	Day 5			X		X			X	

Study measures will be collected by the study CRC (cycle 1) and/or by the study acupuncturists (cycle 2 and 3). The post-acupuncture assessments will be collected by the study acupuncturists. Assessments will be coordinated with ear acupuncture visits when possible, so that patient convenience is maximized. Day 2 and Day 5 assessments will be filled out by the patients at home and returned to the study CRC at the next visit. The home assessments will be put in an envelope to keep the confidentiality. To facilitate completion, patients will be reminded by phone and by email to complete the home assessments. Patients may also choose to complete the home assessments over the phone with the study coordinator.

The following measures will be collected:

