### **7.6 Acupuncture Treatment Form**

An acupuncture treatment form will be generated by the treating acupuncturist at each ear acupuncture treatment. The form will document the following items: acupuncture points used, patient-reported acupuncture intensity, and any acupuncture-related adverse events.

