### **9.2.3 Protocol-Specific Expedited Adverse Event Reporting Exclusions**

For this protocol only, the AEs/grades determined to be related to chemotherapy treatment or the disease under study (i.e. breast cancer) and not the study intervention (ear acupuncture) do not require expedited reporting to the Overall PI or the DFCI IRB. However, they still must be reported through the routine reporting mechanism (i.e. case report form).

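### Adverse events are actively asked about only at acupuncture sessions, so cycle 1 supplies no like-for-like background for non-specific events such as presyncope and syncope

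*Combined protocol and SAP*

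**What the plan says.** Section 8.2 sets the trigger for active questioning: "Individuals receiving the ear acupuncture will be asked about acupuncture-related adverse events at each acupuncture treatment". Section 7.6 ties the paperwork to the same occasion: "An acupuncture treatment form will be generated by the treating acupuncturist at each ear acupuncture treatment". On that form (Appendix V), item 5 reads "Did the patient report any adverse event per CTCAE v4.0 at this visit" and asks for grade and attribution. Its pre-printed terms are skin bruise, hematoma, skin infection, presyncope, syncope and nausea. Section 8.1 says of cycle 1: "No acupuncture will be performed during the first infusion cycle". The Day 2 and Day 5 telephone surveys in Appendix X consist of ESAS, STAI, MAT and the medication log, with no adverse event question.

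Other safety information does reach into cycle 1. Section 9.4 requires all adverse events on the toxicity case report forms. Section 9.2.3 keeps chemotherapy- and disease-related events in routine reporting. Section 5 lists an emergency events diary, and section 3 counts ER visits and hospital admissions over the trial.

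On use of the data, Objective 1 covers the incidence of acupuncture-related side effects. Section 10.4 promises CTCAE reporting for all patients. Section 5, directly after its CTCAE sentence, adds: "Measures will be compared between chemotherapy cycles".

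**The concern.** Each patient serves as her own control: booklet in cycle 1, needles in cycles 2 and 3. Presyncope, syncope and nausea can all occur at a chemotherapy infusion without needles. Sections 8.2 and 9.1 ask for a judgement of relatedness for each event, and that judgement is easier when the frequency of the same event without needles is known from the same question. As written, the question comes with the needles, so asking and exposure start together.

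Two things are at stake. Attribution under Objective 1 lacks a like-for-like background for the non-specific events other than nausea. And a table of events by cycle, if one is made, would mix elicited events in cycles 2 and 3 with events that reached the case report form some other way in cycle 1.

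**Working it through.** The plan states no figure on this point, so the main check sets its sections side by side.

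**Which sources of adverse event information are described for each cycle**
- Active CTCAE question with grade and attribution (8.2, 7.6, Appendix V item 5): cycles 2 and 3 only, because section 8.1 places no acupuncture in cycle 1. With 26 patients and full attendance, that is 2 × 26 = 52 of 52 acupuncture infusions and 0 of 26 cycle 1 infusions. A make-up session under 8.1 moves the form with the needles and does not change this.
- Toxicity case report forms (9.4, 9.2.3): all cycles. These sections say what must be reported, not who asks the patient in cycle 1 or when.
- Emergency events diary, ER visits and admissions (5, 3): all cycles, but limited to events that lead to emergency care.
- ESAS (7.1, four times per cycle) and MAT (7.3, Day 2 and Day 5): all cycles. They cover nausea, and MAT also covers vomiting. Neither asks about presyncope or syncope.

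So what is missing in cycle 1 is a common method of elicitation, and it matters chiefly for presyncope and syncope.

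**What follows if events are shown by cycle**

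This is an illustration on assumed inputs. Let the true probability that a patient has an event be p in every cycle, so that needles have no effect. Let cycle 1 capture a fraction q of what active questioning captures. The expected number of patients with a recorded event is 26 × p in an actively questioned cycle and 26 × p × q in cycle 1, so the apparent ratio is 1/q whatever p is.

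| q (assumed) | Cycle 1, p = 0.10 | Cycle 1, p = 0.20 | Apparent ratio |
|---|---|---|---|
| 1 | 2.6 | 5.2 | 1.0 |
| 0.75 | 1.95 | 3.9 | 1.33 |
| 0.5 | 1.3 | 2.6 | 2.0 |
| 0.25 | 0.65 | 1.3 | 4.0 |

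The comparators in one acupuncture cycle are 26 × 0.10 = 2.6 and 26 × 0.20 = 5.2. The documents give neither p nor q. The table shows the direction of the bias and how it depends on q; it does not estimate its size.

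**When the SAE window opens**

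Section 9.2.1 covers "any serious adverse event (SAE) that occurs after the initial dose of study treatment, during treatment, or within 30 days of the last dose" and does not define study treatment. Section 9.2.3 says that events due to chemotherapy or the disease and "not the study intervention (ear acupuncture) do not require expedited reporting", which points to a start in cycle 2. Section 7 uses the word intervention for the booklet as well: "The post-intervention assessments will be repeated after the completion of reading educational material or acupuncture". The start point is therefore undefined.

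**The case against.** The strongest reply is that no planned analysis is distorted. Section 10.2 confines the contrast of cycle 1 with cycles 2 and 3 to patient-reported outcomes. Section 10.4 carries that through for symptom, anxiety and nausea scores and leaves safety descriptive. Objective 1 concerns acupuncture-related side effects, which cannot occur before the first needle, so asking when needles are used fits it. This stands against any claim that event rates rise by construction, which a reader might infer. The rise needs both a by-cycle display and q below 1. It does not answer the attribution point.

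A reader might also infer that cycle 1 has no safety data. The case report forms, diary, ER and admission data, and the ESAS and MAT nausea scores show otherwise.

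Two sets of figures are tempting and should not be used as the size.
- Section 2.2 reports nausea in about 43% of patients at infusion. Applied here it gives 0.43 × 52 = 22.4 sessions and 0.43 × 26 = 11.2 cycle 1 infusions. That is the same proportion twice and shows no bias. The figure is also per patient, comes from an ear acupuncture service, and concerns the one symptom already covered in cycle 1.
- Cycle 1 makes up 14/(2 × 14 + 5) = 42% or 21/(2 × 21 + 5) = 45% of days to cycle 3 Day 5. But item 5 asks about the visit, so it does not query the days between sessions in cycles 2 and 3 either.

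Two further points stand in part. Section 8.2 asks only about acupuncture-related events whereas item 5 asks about any event; staff who follow the narrower wording would log fewer background events and the asymmetry would shrink. And because cycle order is fixed, a cycle 1 rate differs from later rates in cycle number as well as in needling.

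**Conclusion.** The point holds in a limited form. Active CTCAE questioning is described only where needles are used, so the no-needle cycle has no adverse event data elicited by the same method. The practical gap is in the non-specific events other than nausea. Any by-cycle display would be biased towards more events under acupuncture to the extent that cycle 1 capture is incomplete; the documents do not allow that extent to be estimated.

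This assumes that the toxicity case report forms and Event Log, which are not reproduced, prompt no equivalent cycle 1 question. Table 1 could not be read reliably enough to settle which forms are used in cycle 1, so nothing here rests on it.

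A reader might infer that serious events are reported only from cycle 2. The documents do not establish that: section 9.2.1 concerns expedited reporting, its start is undefined, and 9.4 has no cycle 2 start. Chemotherapy-related events, the likely serious events in cycle 1, are exempt from expedited reporting in any case. That part is a clarification only.

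**What to change.** - Have the study coordinator, who already collects measures in cycle 1 under section 7, complete the Appendix V item 5 checklist at the end of the cycle 1 Day 1 booklet session. Use the same terms, grades and attribution, and the same any-event wording in all three cycles, since the narrower question in 8.2 cannot be asked before needling.
- In section 10.4, tabulate CTCAE events descriptively by cycle from this common query, and state that cycle order is fixed and so confounded with acupuncture.
- Reconcile the start of the SAE window in 9.2.1 with 9.2.3 and section 7, so that one defined starting point is stated.

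The cost is one short checklist at an existing visit, a few more events to log (mostly chemotherapy-related), and a wording change. No visits are added. The resulting background helps in judging relatedness but does not isolate the effect of needling.
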